14. STATISTICAL CONSIDERATIONS

14.1 Study Design/Endpoints

Arm 2: Study design/endpoints are identical for Arms 1 & 2.

In this study of patients with liver lesions, it is expected that roughly two-thirds of patients will have FDG-avid tumors, one-third of patients will have non FDG-avid tumors, and although it is possible for a patient to have both types of tumor, that is considered rare. For sample size and power considerations we therefore conservatively assume that patients will have one type of tumor or the other and therefore target a sample size of 100 patients per arm, allowing for the potential for renal insufficiency in up to 25% of all patients (described in more detail below). Also, as the techniques focus on analysis by tumor and it is estimated that 70% of patients will have only a single lesion, the sample size considerations will focus on enrolling *patients* rather than *tumors*. Multiple tumors per patient, when they occur, will be treated and assessed in the statistical analysis, with appropriate adjustment for clustering of tumors within a patient to account for correlation of responses within a patient. Sample size considerations, however, focus on enrollment of patients. The study design and endpoints are identical for Arm 1 and Arm 2.

Primary Objectives:

1. Among FDG-avid liver tumors, comparison of imaging techniques will be done on paired tumor samples using McNemar's test, focusing on discordant pairs (AP-PET-1 adequate/CECT inadequate and AP-PET-1 inadequate/CECT adequate). For these comparisons it is expected that the rate of discordance will be high (near 60% of all pairs) and that differential in discordance will be large (difference between discordant pairs on the order of 50% or higher). In addition to comparing discordant pairs, there is interest in being able to precisely estimate the visibility rates under each imaging modality. With 50 paired samples in the FDG-avid liver tumor ablation group in each arm, visibility of the entire ablation margin can be estimated with a 95% binomial confidence interval that should be no wider than 24 percentage points (+/- 12%) in the expected range of visibility of each modality (80% for AP-PET and 20% for CECT). This sample size will provide greater than 90% power for McNemar's test using a 5% type I error given the assumptions above about discordance.

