Since both imaging modalities are required for McNemar's test and the rate of renal insufficiency that would preclude a paired CECT scan is estimated to be roughly 25%, inflation for loss due to patients with renal insufficiency implies that the FDG-avid tumor target sample size for this trial is 67 patients per arm ($=50/0.75$). The trial will be monitored closely for

CONFIDENTIAL

This document is confidential. Do not disclose or use except as authorized.

potential early closure if the rate of renal insufficiency is lower than 25% or potential extension of accrual if the yield of paired samples is lower than 75%.

2. With at least 50 evaluations in the FDG-avid liver tumor treated group per arm, the visibility rates for AP-PET-1 and intra-procedural PET/CECT will be estimated with an accuracy of +/- 12% using 95% confidence intervals for binomial proportions. With this sample size, if the observed visibility rate is near 90%, the 95% confidence interval width is expected to be shorter than 19 percentage points.

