3. In patients with FDG-avid liver tumors, the goal of this objective is to assess the proportion of cases confirmed to have adequate ablation margins using 24-hour MRI or CT as the gold standard among those identified as nominally adequate at the time of final intra-procedural imaging. Note that for this objective, patients do not have to receive intra-procedural iodinated IV contrast, hence the reduction in sample size due to renal insufficiency does not apply to this objective. It is expected that nearly 95% of cases will be identified as nominally adequate by all available post-ablation intra-procedural imaging data (i.e. standard-of-care imaging plus AP-PET). With 75 cases per arm, this translates to roughly 71 nominally adequate cases. Among these cases, the ablation margin adequacy rates based on 24-hour MRI or CT will be estimated with 95% binomial confidence intervals and it is expected that the adequacy rates for all available post-ablation intra-procedural imaging will be high, in the range of 90% or higher. With the sample size stated above, the 95% confidence intervals to confirm adequate ablation after 24 hours will be no wider than 16 percentage points (+/- 8%). It is also of interest to confirm that margins that were deemed inadequate on AP-PET alone were confirmed inadequate based on 24-hour MRI or CT but this objective is largely exploratory since the sample size for cases labeled inadequate after AP-PET is expected to be very low, only 5% of the total cases. Finally, it is of interest to assess agreement of final intra-procedural AP-PET with 24-hour MRI or CT. Concordance rates are unknown but are estimated to be in the range of 50 to 80%. With 75 cases per arm, the 95% confidence intervals on the concordance rates are expected to be no wider than 24 percentage points (+/- 12%) assuming, conservatively, that the true concordance rate is near 50%.

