4. Among non FDG-avid tumors (expected to be one-third of patient accrual) comparison of imaging techniques will be done on paired samples using McNemar's test, focusing on discordant pairs (AP-PET fused to pre-procedural MRI or CT adequate/CECT fused to pre-procedural MRI or CT inadequate and AP-PET fused to pre-procedural MRI or CT inadequate/CECT fused to pre-procedural MRI or CT adequate). For these comparisons it is expected that the rate of discordance will be high (near 70% of all pairs) and that differential in discordance will be large (difference between discordant pairs on the order of 60%). In addition to comparing discordant pairs, there is interest in being able to precisely estimate the visibility rates under each imaging modality. With 25 paired samples per arm in the non FDG-avid liver tumor ablation group, visibility of the entire ablation margin can be estimated with a 95% binomial confidence interval that should be no wider than 34 percentage points (+/- 17%) in the expected range of visibility of each modality (80% for AP-PET and 20% for CECT). This sample size will provide greater than 90% power for McNemar's test using a 5% type I error given the assumptions above about discordance.

CONFIDENTIAL

This document is confidential. Do not disclose or use except as authorized.

Since both imaging modalities are required for McNemar's test and the rate of renal insufficiency that would preclude a paired CECT scan is estimated to be roughly 25%, inflation for loss due to patients with renal insufficiency implies that the non FDG-avid tumor target sample size for this trial is 33 patients per arm ($=25/0.75$). The trial will be monitored closely for potential early closure if the rate of renal insufficiency is lower than 25% or potential extension of accrual if the yield of paired samples is lower than 75%.

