5. In patients with non FDG-avid liver tumors, the goal of this objective is to assess the proportion of cases confirmed to have adequate ablation margins using 24-hour MRI or CT as the gold standard among those identified as nominally adequate at the time of final intra-procedural imaging. Patients evaluated for this objective do not have to receive intra-procedural iodinated IV contrast. It is expected that nearly 95% of cases will be identified as nominally adequate by all available post-ablation intra-procedural imaging data (i.e. standard-of-care imaging plus AP-PET). With 33 cases per arm, this translates to roughly 31 nominally adequate cases. Among these cases, the ablation margin adequacy rates based on 24-hour MRI or CT will be estimated with 95% binomial confidence intervals and it is expected that the adequacy rates for all available post-ablation intra-procedural imaging will be high, in the range of 90% or higher. With the sample size stated above, the 95% confidence intervals to confirm adequate ablation after 24 hours will be no wider than 24 percentage points ($\pm 12\%$). It is also of interest to confirm that margins that were deemed inadequate on AP-PET fused to pre-procedural MRI or CT were confirmed inadequate based on 24-hour MRI or CT but this objective is largely exploratory since the sample size for cases labeled inadequate after AP-PET fused to pre-procedural MRI or CT is expected to be very low, only 5% of the total cases. Finally, it is of interest to assess agreement of final intraprocedural AP/FDG PET fused to pre-procedural MRI or CT with 24-hour MRI or CT. Concordance rates are unknown but are estimated to be in the range of 50 to 80%. With 33 cases per arm, the 95% confidence intervals on the concordance rates are expected to be no wider than 36 percentage points ($\pm 18\%$) assuming, conservatively, that the true concordance rate is near 50%.

Secondary Objectives:

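### Primary Objective 3 computes its precision from 75 FDG-avid cases per arm, but the plan's own target is 67; the maximum concordance interval width becomes 25 points, not 24

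*Combined protocol and SAP*

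**What the plan says.** Section 14.1 builds each arm from two groups that do not overlap. It expects that "roughly two-thirds of patients will have FDG-avid tumors" and one-third will not, assumes one tumour type per patient for sizing, and on that basis will "therefore target a sample size of 100 patients per arm". Section 14.2 repeats 100 per arm.

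The group targets come from the paired comparisons, each inflated for 25% renal insufficiency:

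- Objective 1: "FDG-avid tumor target sample size for this trial is 67 patients per arm", from 50 pairs.
- Objective 4: "non FDG-avid tumor target sample size for this trial is 33 patients per arm", from 25 pairs.

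Objective 3 (FDG-avid tumours, intra-procedural result against 24-hour MRI or CT) does not need intra-procedural contrast, "hence the reduction in sample size due to renal insufficiency does not apply to this objective". It then says "With 75 cases per arm, this translates to roughly 71 nominally adequate cases", with an adequacy interval of at most 16 points at 90% or higher, and "With 75 cases per arm, the 95% confidence intervals on the concordance rates are expected to be no wider than 24 percentage points" at a true rate near 50%.

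Objective 5, the non-FDG-avid counterpart, uses its own group target: "With 33 cases per arm, this translates to roughly 31 nominally adequate cases".

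**The concern.** Exempting Objective 3 from the renal loss brings its number back from 50 pairs to the 67 FDG-avid patients enrolled. It cannot raise it above 67. With 75 the two groups no longer fit in the arm, and a reader cannot tell whether 67 or 75 FDG-avid patients were planned.

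Objective 3 is listed as primary, and the only statistical support offered for its case number is interval width. If the input is too large, the promised precision is better than the planned enrolment can deliver.

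**Working it through.** **Inputs (all section 14.1).** 100 patients per arm; two-thirds FDG-avid; 50 and 25 pairs; 25% renal insufficiency; 95% nominally adequate; confirmed adequacy 90% or higher; concordance 50% as the conservative case.

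**1. Case numbers.**
- FDG-avid target: 50/0.75 = 66.7, so 67. Check: 100 × 2/3 = 66.7.
- Sum of the groups: 67 + 33 = 100. With 75 instead: 75 + 33 = 108.
- Nominally adequate, plan's input: 0.95 × 75 = 71.25, about 71 as stated.
- Nominally adequate, planned target: 0.95 × 67 = 63.65, about 64.
- Parallel check, Objective 5: 0.95 × 33 = 31.35, about 31 as stated.

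The step from 75 to 71 is correct. The input is what is wrong.

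**2. Which interval the plan used.** The text says only that the intervals are binomial. Two candidates are:
- Exact (Clopper-Pearson): lower limit = Beta quantile 0.025 with parameters (x, n − x + 1); upper limit = Beta quantile 0.975 with parameters (x + 1, n − x).
- Wald: width = 2 × 1.96 × √(p(1 − p)/n).

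The table uses the attainable count nearest the plan's rate for the exact interval, and the plan's rate itself for Wald. Widths are in percentage points.

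| Objective | x/n | Stated | Exact | Wald |
|---|---|---|---|---|
| 1 | 40/50 | 24 | 23.7 | 22.2 |
| 2 | 45/50 | under 19 | 18.5 | 16.6 |
| 3, adequacy | 64/71 | 16 | 15.2 | 14.0 |
| 3, concordance | 38/75 | 24 | 23.6 | 22.6 |
| 4 | 20/25 | 34 | 33.9 | 31.4 |
| 5, adequacy | 28/31 | 24 | 23.7 | 21.1 |
| 5, concordance | 17/33 | 36 | 35.7 | 34.1 |

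Rounded up to the next whole point, the exact interval gives the stated figure in all seven rows, and Wald in none. The plan's widths therefore follow the exact interval, and both Objective 3 widths reproduce from its own 75 and 71.

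**3. The same rule at the planned numbers.**
- Concordance, 34/67: exact interval 38.2% to 63.2%, width 24.9, so 25 against the stated 24. At 50%, Wald gives 23.9 and Wilson 23.3.
- Over the plan's expected 50–80% range at n = 67, the exact width is 24.2 at 42/67 (63%), 24.0 at 43/67 (64%), and 20.1 at 54/67 (81%).
- Smallest n with an exact width of 24.0 or less at 50%: 72 gives 24.05 and 73 gives 23.9, so 73.
- Adequacy, 58/64 (90.6%, the first count at or above 90%): exact interval 80.7% to 96.5%, width 15.8. The 16-point limit holds.

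**4. Power claims.** These depend on 50 and 25 pairs, not on 75. Exact McNemar power is 99.9% with 50 pairs (discordant cells 0.55 and 0.05) and 98.4% with 25 pairs (0.65 and 0.05). Both exceed the claimed 90%.

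**The case against.** **The 25-point result depends on the interval method.** The plan does not name one, its widths are worded as upper limits, and Wald satisfies all seven of them. Under Wald or Wilson the 24-point statement is still true at 67. This stands as a limit on the consequence. It does not touch the contradiction between 75 and 67, which needs no interval at all.

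**67 is not a fixed number.** Objective 1 allows early closure if renal insufficiency is below 25%, and extension if fewer than 75% of patients yield pairs. Suppose accrual stopped at 50 pairs. With an assumed 15% renal rate there would be about 50/0.85 = 59 cases (exact width 26.6); with 10%, about 50/0.90 = 56 (27.3). This stands, and means the corrected width should be tied explicitly to 67 cases. Early closure moves the number further from 75; extension could raise it, but the plan does not size Objective 3 on an extended accrual.

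**Analysis is by tumour.** The mix in section 1.1 (70/15/10/5%, counting more than three as four) averages 1.5 tumours per patient, or about 100 from 67 patients. With a design effect of 1 + ICC, the effective number reaches 73 if the intra-patient correlation is about 0.38 or less (100.5/1.38 = 73). The plan gives no correlation, so this is an assumption. Achieved precision could therefore be better than the one-tumour-per-patient figure. But section 14.1 sizes by patients, and a tumour count would be about 100, so this does not explain 75.

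**The origin of 75 is unexplained, so 67 may not be the number to keep.** True in principle. But 67 agrees with the group targets, the two-thirds split and the arm total, and 75 agrees with none of them.

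**Conclusion.** Wrong as written. Objective 3 should rest on 67 FDG-avid cases per arm and about 64 nominally adequate, not 75 and 71. This follows from the plan's own targets and does not depend on the interval method.

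The consequence is small. At 50% concordance the exact width rises from 23.6 to 24.9 points, a loss of 1.4 points before rounding (24.94 − 23.55), and passes the stated maximum by about one point. That rests on the exact interval, one tumour per patient, and accrual that reaches 67. The adequacy width, the McNemar power and all decision rules are unaffected. It should be fixed because a primary objective carries a wrong sample size and a precision figure derived from it.

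**What to change.** In section 14.1, Objective 3:

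- Replace 75 with 67 in both places, and 71 with 64.
- State the concordance width as no wider than 25 points (±12.5) at 67 cases, so that the limit is read as conditional on reaching that number.
- Leave the adequacy width at 16 points (±8).
- Name the exact (Clopper-Pearson) interval, which is the one the stated widths already follow.

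If 75 was intended, the alternative is to justify it and raise the per-arm target to match.

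As a separate matter, the front sheet (Subject Population) gives a study-wide enrolment goal of 75, while sections 14.1 and 14.2 give 100 per arm and 200 in total. These need to be reconciled; if 75 is the true total, all power and precision statements must be redone for it.

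The Objective 3 change costs only text: no added patients, no change to the design, closure rule or power statements, and one stated width one point less favourable.

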14.2 Sample Size/Accrual Rate

Target enrollment for each arm of the study is 100 patients. Each patient will be followed for 12 months after their study procedure(s). An accrual rate of 3-6 subjects/month is anticipated. Enrollment of 200 total patients is expected to be completed within 3-4 years.

14.3 Stratification Factors – N/A

14.4 Analysis of Secondary Endpoints

See above, Section 14.1

14.5 Reporting and Exclusions

This is not a therapeutic drug trial. Please see Section 14.1

15. PUBLICATION PLAN

The principal investigator holds primary responsibility for publication of the results of this study. The study results will be submitted for publication in a peer-reviewed journal within 24 months of the end of data collection, regardless of the outcomes.

CONFIDENTIAL

This document is confidential. Do not disclose or use except as authorized.

17. APPENDICES

CONFIDENTIAL

This document is confidential. Do not disclose or use except as authorized.

CONFIDENTIAL

This document is confidential. Do not disclose or use except as authorized.

Perfusion PET Assessment of Liver Tumor Ablations

Version 6/9/2014

Appendix A: Performance Status Criteria

ECOG Performance Status Scale		Karnofsky Performance Scale	
Grade	Description	Percent	Description
0	Normal activity. Fully active, able to carry on all pre-disease performance without restriction.	100	Normal, no complaints, no evidence of disease.
		90	Able to carry on normal activity; minor signs or symptoms of disease.
1	Symptoms, but ambulatory. Restricted in physically strenuous activity, but ambulatory and able to carry out work of a light or sedentary nature (e.g., light housework, office work).	80	Normal activity with effort; some signs or symptoms of disease.
		70	Cares for self, unable to carry on normal activity or to do active work.
2	In bed < 50% of the time. Ambulatory and capable of all self-care, but unable to carry out any work activities. Up and about more than 50% of waking hours.	60	Requires occasional assistance, but is able to care for most of his/her needs.
		50	Requires considerable assistance and frequent medical care.
3	In bed >50% of the time. Capable of only limited self-care, confined to bed or chair more than 50% of waking hours.	40	Disabled, requires special care and assistance.
		30	Severely disabled, hospitalization indicated. Death not imminent.
4	100% bedridden. Completely disabled. Cannot carry on any self-care. Totally confined to bed or chair.	20	Very sick, hospitalization indicated. Death not imminent.
		10	Moribund, fatal processes progressing rapidly.
5	Dead.	0	Dead.

CONFIDENTIAL

This document is confidential. Do not disclose or use except as authorized.
